6.1.2 Management of Hypersensitivity Reaction

Table 1: Management of allergic reaction/hypersensitivity based on CTCAE Grade

Description	Action
Grade I Allergic Reaction/Hypersensitivity: (Transient flushing or rash, drug fever < 38°C):	Supervise without further treatment for allergic reaction/hypersensitivity.
Grade 2 Hypersensitivity Reaction: (Rash, flushing, dyspnea, urticaria, drug fever greater than or equal to 38°C) and/or asymptomatic bronchospasm:	Interrupt the infusion. If symptoms abate, attempt re-infusion at a slower rate. If the symptoms recur, discontinue infusion and follow for recurrent allergic reaction/hypersensitivity in the next paragraph.
Recurrent Grade 2 or Grade 3 or 4 Hypersensitivity Reaction:	Stop the infusion. Administer additional doses of H1 and H2 blockers intravenously. Administer IV steroids and consider epinephrine and bronchodilators as clinically indicated.
Grade 3 or 4 Hypersensitivity Reaction:	Will be permanently discontinued from study treatment.

Prior to re-challenge of Grade 2 allergic reaction/HSR and if there is a subsequent cycle, the following prophylactic premedications are recommended prior to the pembrolizumab infusion: give both an H1 and H2 blocker intravenously within 30 to 60 minutes before pembrolizumab infusion. If treatment delay necessitates a period longer than 12 weeks, treatment is stopped and the subject is discontinued from the study.

6.1.3 Dose Modification for Toxicity

Adverse events (both non-serious and serious) associated with pembrolizumab exposure may represent an immunologic etiology. These adverse events may occur shortly after the first dose or several months after the last dose of treatment. Pembrolizumab must be withheld for drug-related toxicities and severe or life-threatening AEs as per Table 2 below.

Table 2: Dose Modification and Toxicity Management Guidelines for Immune-related AEs Associated with Pembrolizumab

General instructions:				
Immune-related AEs	Toxicity grade or conditions (CTCAEv4.0)	Action taken to pembrolizumab	irAE management with corticosteroid and/or other therapies	Monitor and follow-up
Pneumonitis	Grade 2	Withhold	
 Administer corticosteroids (initial dose of 1-2 mg/kg prednisone or equivalent) followed by taper 	
 Monitor participants for signs and symptoms of pneumonitis Evaluate participants with suspected pneumonitis with radiographic imaging and initiate corticosteroid treatment Add prophylactic antibiotics for opportunistic infections
	Grade 3 or 4, or recurrent Grade 2	Permanently discontinue		
Diarrhea / Colitis	Grade 2 or 3	Withhold	
 Administer corticosteroids (initial dose of 1-2 mg/kg prednisone or equivalent) followed by taper 	
 Monitor participants for signs and symptoms of enterocolitis (ie, diarrhea, abdominal pain, blood or mucus in stool with or without fever) and of bowel perforation (ie, peritoneal signs and ileus). Participants with \geq Grade 2 diarrhea suspecting colitis should consider GI consultation and performing endoscopy to rule out colitis. Participants with diarrhea/colitis should be advised to drink liberal quantities of clear fluids. If sufficient oral fluid intake is not feasible, fluid and electrolytes should be substituted via IV infusion.
	Grade 4	Permanently discontinue		

AST / ALT elevation or Increased bilirubin	Grade 2	Withhold	
 Administer corticosteroids (initial dose of 0.5- 1 mg/kg prednisone or equivalent) followed by taper 	
 Monitor with liver function tests (consider weekly or more frequently until liver enzyme value returned to baseline or is stable)
	Grade 3 or 4	Permanently discontinue	
 Administer corticosteroids (initial dose of 1-2 mg/kg prednisone or equivalent) followed by taper 	
Type 1 diabetes mellitus (T1DM) or Hyperglycemia	Newly onset T1DM or Grade 3 or 4 hyperglycemia associated with evidence of β -cell failure	Withhold	
 Initiate insulin replacement therapy for participants with T1DM Administer anti-hyperglycemic in participants with hyperglycemia 	
 Monitor participants for hyperglycemia or other signs and symptoms of diabetes.
Hypophysitis	Grade 2	Withhold	
 Administer corticosteroids and initiate hormonal replacements as clinically indicated. 	
 Monitor for signs and symptoms of hypophysitis (including hypopituitarism and adrenal insufficiency)
	Grade 3 or 4	Withhold or permanently discontinue ¹		
Hyperthyroidism	Grade 2	Continue	
 Treat with non-selective beta-blockers (eg, propranolol) or thionamides as appropriate 	
 Monitor for signs and symptoms of thyroid disorders.
	Grade 3 or 4	Withhold or permanently discontinue ¹		
Hypothyroidism	Grade 2-4	Continue	
 Initiate thyroid replacement hormones (eg, levothyroxine or liothyroinine) per standard of care 	
 Monitor for signs and symptoms of thyroid disorders.
Nephritis and Renal dysfunction	Grade 2	Withhold	
 Administer corticosteroids (prednisone 1-2 mg/kg or equivalent) followed by taper. 	
 Monitor changes of renal function
	Grade 3 or 4	Permanently discontinue		
Myocarditis	Grade 1 or 2	Withhold	
 Based on severity of AE administer corticosteroids 	
 Ensure adequate evaluation to confirm etiology and/or exclude other causes
	Grade 3 or 4	Permanently discontinue		

All other immune-related AEs	Intolerable/persistent Grade 2	Withhold	
 Based on type and severity of AE administer corticosteroids 	
 Ensure adequate evaluation to confirm etiology and/or exclude other causes
	Grade 3	Withhold or discontinue based on the type of event. Events that require discontinuation include and not limited to: Gullain-Barre Syndrome, encephalitis		
	Grade 4 or recurrent Grade 3	Permanently discontinue		

1. Withhold or permanently discontinue pembrolizumab is at the discretion of the investigator or treating physician.

NOTE:
For participants with Grade 3 or 4 immune-related endocrinopathy where withhold of pembrolizumab is required, pembrolizumab may be resumed when AE resolves to \leq Grade 2 and is controlled with hormonal replacement therapy or achieved metabolic control (in case of T1DM).

6.2 Dose Delays for HD IL-2

6.2.1 Start of New Cycle

A new treatment cycle will only be initiated when all of the following conditions are met:

- ANC $\geq 1,500 \times 10^9/L$
- Platelets $\geq 100 \times 10^9/L$
- Non-hematologic treatment related toxicities have improved to \leq Grade 1 or to the subject's baseline values (except alopecia)

If blood counts are below this threshold (first two bullet points), blood work is to be repeated weekly until counts are at an acceptable level. If treatment is unable to restart within 12 weeks of the planned treatment date, the subject will be permanently discontinued from study therapy.

6.2 Protocol Therapy Discontinuation

In addition to discontinuation from therapy related to toxicities as outlined above, a subject will also be discontinued from protocol therapy and followed per protocol under the following circumstances outlined below. The reason for discontinuation of protocol therapy will be documented on the electronic case report form (eCRF)

- Documented disease progression
- Site investigator determines a change of therapy would be in the best interest of the subject
- Subject requests to discontinue protocol therapy, whether due to unacceptable toxicity or for other reasons
 - In a subject decides to prematurely discontinue protocol therapy (“refuses treatment”), the subject should be asked if he or she may still be contacted for further scheduled study assessments. The outcome of that discussion should be documented in both the medical records and in the eCRF.
- Female subject becomes pregnant
- HD IL-2 will be discontinued if there is a ≥ 12 -week delay between cycles
- Pembrolizumab will be discontinued if there is a ≥ 12 -week delay between cycles

6.3 Protocol Discontinuation

If a subject decides to discontinue from the protocol (and not just from protocol therapy) all efforts should be made to complete and report study assessments as thoroughly as possible. A complete final evaluation at the time of the subject's protocol withdrawal should be made with an explanation of why the subject is withdrawing from the protocol. If the reason for removal of a subject from the study is an adverse event, it will be recorded on the eCRF.

7. STUDY CALENDAR & EVALUATIONS

Study Evaluations Cycle = 21 days for Pembrolizumab Cycle = 5 days for HD IL-2	Screening	Cycles 1-2 Pembrolizumab (P)	End of Cycle 2 Pembro	Cycle 1 HD IL2	Cycle 2 HD IL2	Safety follow up visit ¹¹	Long-term Follow up ¹²
	-28 days	Day 1 (± 3 days)	Day 21 (± 3 days)	Days 1-5	Days 15-19	28 days post last dose (± 7 days)	Every 3 months (±14 days)
REQUIRED ASSESSMENTS							
Informed Consent/HIPPA authorization	X						
Medical History ¹	X						
Diagnosis and Staging ²							
Physical Exam	X	X	X	X	X	X	
Vital signs and ECOG Performance Status ³	X	X	X	X	X	X	
AEs & concomitant medications	X	X	X	X	X	X	
LABORATORY ASSESSMENTS							
Complete Blood Cell Count with diff (CBC)	X	X ¹⁰	X	X	X	X	
Comprehensive Metabolic Profile (CMP)	X	X ¹⁰	X	X	X	X	
PT/INR and aPTT	X	X ¹⁰					
Thyroid Function (TSH, T4, free T3)	X		X				
Vitamin D level	X						
Pregnancy test (serum or urine) (WOCBP) ⁴	X	X ⁴					
Urinalysis	X	X ¹⁰	X		X		
DISEASE ASSESSMENT							
Chest X-ray				X			
CT of chest ⁵	X		X			X	
CT or MRI of abdomen and pelvis ⁵	X		X			X	
CT or MRI Brain ⁵	X		X			X	
TREATMENT EXPOSURE							
Pembrolizumab		X					
HD IL-2				X	X		
SPECIMEN COLLECTION							
Archival Tumor Tissue ⁶	X						
Blood Samples ⁷		X ⁷	X	X	X ⁷		
Stool sample ⁸		X					

Study Evaluations Cycle = 21 days for Pembrolizumab Cycle = 5 days for HD IL-2	Screening	Cycles 1-2 Pembrolizumab (P)	End of Cycle 2 Pembro	Cycle 1 HD IL2	Cycle 2 HD IL2	Safety follow up visit ¹¹	Long-term Follow up ¹²
	-28 days	Day 1 (± 3 days)	Day 21 (± 3 days)	Days 1-5	Days 15-19	28 days post last dose (± 7 days)	Every 3 months (±14 days)
BANKING SAMPLES							
Whole blood, Plasma and PBMCs ⁹		X ⁹	X			X	
FOLLOW-UP							
Survival Status, Subsequent Therapy							X

Key to Footnotes

CBC with differential and platelet to include: Hgb, Hct, WBC, ANC, lymphocyte count, platelets. CMP to include sodium, potassium, chloride, creatinine, blood urea nitrogen; liver function tests (LFTs) to include AST, ALT, total bilirubin, alkaline phosphatase

1: Medical History to include documentation of prior anti-cancer treatment including medications (chemotherapy, checkpoint inhibitors, etc.), radiation, or surgery. A question of how the subject learned about the study will be asked.

2: Diagnosis and staging to include pathology report and Tumor Node Metastasis (TNM) staging.

3: Vital signs to include blood pressure, weight, and height (screening only) and ECOG performance status.

4: For women of childbearing potential (WOCBP): urine or serum βhCG if clinically appropriate will be done during screening and within 72 hours of initiation of study treatment. If a urine test is done and it is positive or cannot be confirmed as negative, a serum pregnancy test will be required.

5: Appropriate scans including CT chest, abdomen/pelvis to assess disease status will be obtained within 4 weeks before initiation of study treatment (screening). Post treatment scans will be performed on Cycle 2 Day 21 (end of Cycle 2 pembrolizumab; +3 days) of pembrolizumab and Cycle 2 of HD IL-2; +9 days) of HD IL-2 including CT chest, abdomen/pelvis. CT or MRI of the brain should be done if clinically indicated at site investigator's discretion.

6: Required if available: submission of unstained slides from archived tumor tissue for PD-L1 expression are to be identified during screening and submitted after the patient is registered to the trial prior to Cycle 2 of pembrolizumab. If archived tumor tissue is not available, the patient does not need to undergo a biopsy to obtain tissue and is still eligible for study.

7: Required: submission of blood for serum (soluble PD-L1, Th1/Th2 ratio and arginine levels) will be collected pre-dose Cycle 1 Day 1 of pembrolizumab, and on Cycle 2 Day 21 (+3 days) of pembrolizumab. Blood samples for these levels will also be collected at the end of each of the HD IL-2 cycles; End of Cycle 1 sample will be drawn (+3 days) prior to dosing Cycle 1 Day 5 (after completion of HD IL-2). The end of Cycle 2 sample will be drawn (+ 9 days) at the end of Cycle 2 Day 19 (after completion of HD IL-2).

- 8: Required: submission of a stool specimen (for microbiome characterization) will be collected at baseline (pre-dose Cycle 1 Day1 of pembrolizumab). Stool for microbiome analysis will be performed prior to treatment. Subjects will be provided a kit with detailed instructions regarding collection of the sample prior to the timepoint it is due. Please see the CLM for additional details.
- 9: Optional: submission of whole blood, plasma and PBMCs for banking to be collected at baseline pre-dose Cycle 1 Day 1 of pembrolizumab and on Cycle 2 Day 21 (+3 days) of pembrolizumab. This sample will also be collected about 4 weeks after the last dose of HD IL-2 (safety visit)
- 10: For Cycle 1 Day of pembrolizumab only: labs do not need to be repeated if done within 7 days of Day 1.
- 11: The safety follow-up visit should occur when subjects permanently stop study treatment for whatever reasons (toxicity, progression, or at discretion of site investigator) and should be performed 30 days (± 7 days) after the last dose of treatment. Subjects who have an ongoing Grade \geq 2 or serious AE (SAE) at this visit will continue to be followed until the AE resolves to \leq Grade 1 or baseline, deemed clinically insignificant, and/or until a new anti-cancer treatment starts, whichever is earlier.
- 12: Long-term follow up will occur in all subjects after the safety follow up visit. Subjects who discontinue treatment for any reason will be followed every 3 months for 12 months. Follow up may be accomplished via clinic visit, phone call, or other avenues as appropriate.

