5.1 Pembrolizumab Administration

Subjects will receive 200 mg pembrolizumab every 3 weeks for two cycles. Cycle length is 21 days (i.e., 3 weeks). On the last day of Cycle 2 (+ 3 days), disease status will be assessed via imaging. Following the pembrolizumab treatment, HD IL-2 treatment will commence.

Correlative research analyses during pembrolizumab administration include examining the relationship between clinical response at the end of Cycle 2 with PD-L1 expression of the archived diagnostic tumor tissue. Research analyses also include examining the relationship between changes in soluble PD-L1 level and Type 1 T helper cell/Type 2 T helper cell (Th1/Th2) ratios during therapy (assessed after the 2nd dose) relative to baseline and characterization of intestinal microbiome to the best clinical response (RECIST 1.1 criteria) and to treatment outcome.

Drug	Dose	Route	Schedule	Cycle Length
Pembrolizumab	200 mg	Intravenously (IV) over 30 minutes	Day 1 of each cycle	3 weeks (21 days)

¹ A window of - 1 or + 2 days may be applied to all study visits to accommodate observed holidays, inclement weather, scheduling conflicts etc. Date and time of each drug administration should be clearly documented in subject's chart and electronic case report forms (eCRFs).

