- For **Grade 2 diarrhea/colitis** that persists greater than 3 days, administer oral corticosteroids.
- For **Grade 3 or 4 diarrhea/colitis** that persists > 1 week, treat with intravenous steroids followed by high dose oral steroids.
- When symptoms improve to Grade 1 or less, steroid taper should be started and continued over no less than 4 weeks.
- For guidelines on treatment holds, timing for restarting treatment or discontinuing treatment permanently, see Section 6.1.3, Table 2.

Type 1 diabetes mellitus (if new onset, including diabetic ketoacidosis [DKA]) or \geq Grade 3 Hyperglycemia, if associated with ketosis (ketonuria) or metabolic acidosis

- For **T1DM or Grade 3-4 Hyperglycemia**
 - Insulin replacement therapy is recommended for Type I diabetes mellitus and for Grade 3-4 hyperglycemia associated with metabolic acidosis or ketonuria.
 - Evaluate patients with serum glucose and a metabolic panel, urine ketones, glycosylated hemoglobin, and C-peptide.

Hypophysitis

- For **Grade 2** events, treat with corticosteroids. When symptoms improve to Grade 1 or less, steroid taper should be started and continued over no less than 4 weeks. Replacement of appropriate hormones may be required as the steroid dose is tapered.
- For **Grade 3-4** events, treat with an initial dose of IV corticosteroids followed by oral corticosteroids. When symptoms improve to Grade 1 or less, steroid taper should be started and continued over no less than 4 weeks. Replacement of appropriate hormones may be required as the steroid dose is tapered.
- For guidelines on treatment holds, timing for restarting treatment or discontinuing treatment permanently, see Section 6.1.3, Table 2.

Hyperthyroidism or Hypothyroidism

Thyroid disorders can occur at any time during treatment. Monitor patients for changes in thyroid function (at the start of treatment, periodically during treatment, and as indicated based on clinical evaluation) and for clinical signs and symptoms of thyroid disorders.

- **Grade 2** hyperthyroidism events (and **Grade 2-4** hypothyroidism):
 - In hyperthyroidism, non-selective beta-blockers (e.g. propranolol) are suggested as initial therapy.
 - In hypothyroidism, thyroid hormone replacement therapy, with levothyroxine or liothyroinine, is indicated per standard of care.
- **Grade 3-4** hyperthyroidism

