5.3.1 Allowed Concomitant Medications

All treatments that the investigator considers necessary for a subject's welfare may be administered at the discretion of the investigator in keeping with the community standards of medical care. All concomitant medications will be recorded on the electronic case report form (eCRF).

All concomitant medications received within 28 days before the first dose of trial treatment and 30 days after the last dose of trial treatment should be recorded. Concomitant medications administered beyond 30 days after the last dose of trial treatment should be recorded for SAEs and ECIs.

Myeloid growth factors to treat subjects with neutropenia according to the American Society of Clinical Oncology (ASCO) Guidelines are permitted. Myeloid growth factors should be avoided (if medically appropriate) in Cycle 1 until subjects have developed a dose-limiting Grade 4 neutropenia.

Antiemetic agents may be administered at the discretion of the site investigator but are not commonly required as a prophylactic agent. All other manifestations of the subject's malignancy should be treated at the discretion of the investigator.

Medications with potential central nervous system (CNS) effects are not prohibited in this study, but it is recommended that their use be minimized to avoid confusion in the interpretation of CNS effects should they occur during the course of treatment with pembrolizumab.

In appropriate settings, such as combinations with agents known to produce frequent thrombocytopenia, restricted uses of anticoagulants should be considered.

All other medical conditions should be treated at the discretion of the site investigator in accordance with local community standards of medical care.

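### No thyroid panel is scheduled after HD IL-2; adding one to the existing safety-visit blood draw is a cheap, minor improvement in safety coverage

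*Combined protocol and SAP*

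**What the plan says.** Section 5.1 fixes the pembrolizumab exposure: "Subjects will receive 200 mg pembrolizumab every 3 weeks for two cycles". HD IL-2 follows (Section 5.2), in two five-day cycles on Days 1-5 and 15-19 of the course.

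In the Section 7 calendar the row "Thyroid Function (TSH, T4, free T3") is marked at screening and at the end of Cycle 2 pembrolizumab. The cells for both HD IL-2 cycles, the safety follow-up visit and long-term follow-up are empty, and no footnote adds a panel. CBC and CMP are marked at the safety visit, but the CMP has no thyroid component: "CMP to include sodium, potassium, chloride, creatinine, blood urea nitrogen; liver function tests (LFTs) to include AST, ALT, total bilirubin, alkaline phosphatase".

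Outside the calendar, Section 5.1.2 instructs sites: "Monitor patients for changes in thyroid function (at the start of treatment, periodically during treatment, and as indicated based on clinical evaluation"). Section 10.1.5 names hypo- and hyperthyroidism among the important identified risks of pembrolizumab. Of immune-related events in general, Section 6.1.3 says: "These adverse events may occur shortly after the first dose or several months after the last dose of treatment". Table 2 in that section gives the treatment, including hormone replacement for Grade 2-4 hypothyroidism.

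Under footnote 11, subjects with an ongoing Grade 2 or higher or serious AE "at this visit will continue to be followed until the AE resolves to" Grade 1 or baseline, with other stopping conditions. Long-term contact is lighter (footnote 12): "Follow up may be accomplished via clinic visit, phone call, or other avenues as appropriate". Section 11.2.1 ends AE recording 30 days after HD IL-2 is discontinued.

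**The concern.** A secondary objective is to characterize the safety of the sequence, pembrolizumab followed by HD IL-2. The only post-baseline thyroid panel is taken before HD IL-2 begins, so no scheduled thyroid result reflects exposure to both drugs. The risk is one the protocol names, the protocol says immune-related events can appear late, and it specifies treatment when thyroid dysfunction is found.

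What lacks a scheduled check is dysfunction that arises after day 42 without symptoms that lead someone to order a test. The safety visit is the last calendar column with blood work. The three-monthly scans that Section 12.1 gives subjects with CR, PR or SD carry no laboratory test, and neither does the long-term follow-up column. At stake are early treatment of an individual subject and, to a small degree, completeness of the secondary safety endpoint.

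**Working it through.** This is calendar arithmetic. Inputs: pembrolizumab every 21 days for two doses (5.1); end-of-Cycle-2 visit on Cycle 2 Day 21 (Section 7, 12.1); HD IL-2 Days 1-5 and 15-19 (5.2); safety visit 28 days (calendar column) or 30 days (footnote 11) after the last dose, ±7 days. One assumption is needed, because the documents fix no start day for HD IL-2: it starts on day 43, the earliest nominal day.

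**The plan's own figure.** First dose = day 1; second dose = 1 + 21 = day 22; Cycle 2 Day 21 = 22 + 20 = day 42. Last dose to last panel: 42 - 22 = 20 days, which matches the approximately 20 days in Section 12.1. With the ±3 days in the calendar column it is 17-23 days.

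**Scheduled coverage with a safety-visit panel.**
- Last HD IL-2 day: 43 + 18 = day 61.
- Safety visit: 61 + 28 = day 89, or 61 + 30 = day 91.
- From the day-42 panel: 89 - 42 = 47 days, or 91 - 42 = 49 days. With the window: 47 - 7 = 40 to 49 + 7 = 56 days.
- From the last pembrolizumab dose: 89 - 22 = 67 days, or 91 - 22 = 69 days. With the window: 67 - 7 = 60 to 69 + 7 = 76 days.
- Each day of delay in starting HD IL-2 adds one day. A start on day 57 gives 67 + 14 = 81 to 69 + 14 = 83 days after the last pembrolizumab dose.

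**Subjects who stop after the second pembrolizumab dose.** Safety visit: 22 + 28 = day 50, or 22 + 30 = day 52. That is 50 - 42 = 8 or 52 - 42 = 10 days after the day-42 panel, so the added panel gains little.

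**Is the interval unusual for this plan?** No. Screening labs may precede registration by 28 days (3.1), and therapy must start within 7 business days of registration (Section 4), taken here as 9-11 calendar days. Screening to day 42 can therefore reach 28 + 9 + 41 = 78 to 28 + 11 + 41 = 80 days. The 47-49 days after day 42 are shorter than that; what differs is that no later scheduled test ends the interval.

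**Fit with AE recording.** The safety visit may fall 28 - 7 = 21 to 30 + 7 = 37 days after the last HD IL-2 dose, while recording under 11.2.1 stops at 30 days. A panel drawn on days 31-37 would fall after recording closes.

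**The case against.** The strongest answer is that the plan already covers the clinical need. Section 5.1.2 calls for periodic and clinically indicated thyroid testing. Physical examination, vital signs and AE review are marked at both HD IL-2 cycles and the safety visit. Table 2 asks for monitoring of signs and symptoms of thyroid disorders. Section 6.2.1 requires treatment-related non-hematologic toxicity to return to Grade 1 or baseline before a new HD IL-2 cycle, and Section 5.3.1 leaves ordinary care open: "All other medical conditions should be treated at the discretion of the site investigator in accordance with local community standards of medical care". All of this stands. Symptomatic thyroid disease should still be found, and the point is confined to scheduled testing of subjects without prompting symptoms.

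The second answer is that much of what a panel would find is not collected. Section 11.2.1 excludes asymptomatic laboratory abnormalities that need no treatment. This also stands in part. Under 11.1.1, however, an abnormality that requires treatment or further tests is an AE, so the panel is not pointless.

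Third, one more panel does not reach the months-later onset that Section 6.1.3 describes, and that sentence concerns immune-related events generally rather than thyroid disease. Both remarks are right and limit the benefit.

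Finally, the HD IL-2 guidelines cited in 5.2, the Study Procedures Manual (5.2.1) and the Investigator's Brochure (10.1.5) may contain more monitoring. They were not available, so the finding concerns the calendar as written.

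**Conclusion.** The point holds as a minor, optional improvement. The calendar schedules no thyroid panel after day 42, hence none after HD IL-2. Adding one at the safety visit would extend scheduled coverage from 20 to 67-69 days after the last pembrolizumab dose for subjects who complete HD IL-2, given a day-43 start. The benefit is largely confined to those subjects.

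Three stronger readings are tempting, and the documents support none of them. A reader might infer that the calendar breaches Section 5.1.2. It does not: a baseline test, one on-study test and clinically indicated testing are a reasonable reading of that text. A reader might infer that cases will be missed or left untreated. The documents give no rate for late asymptomatic dysfunction, for how often it reaches Grade 2, or for how often it needs treatment, so the figures above are days without a scheduled test and nothing more. A reader might also infer that one added panel closes the gap. It only narrows it, since later onset remains without a scheduled test.

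Thyroid results play no part in the response definition, so the primary endpoint, the Simon stopping rule and the sample size are unaffected. Confidence in the calendar reading is high; the clinical size of the benefit is unknown.

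**What to change.** In the Section 7 calendar, mark the existing thyroid-function row at the safety follow-up visit, on the blood already drawn for CBC and CMP. Preferably draw it within 30 days of the last HD IL-2 dose, early enough for the result to return inside the 11.2.1 recording window. Leave the rules in 11.1.1 and 11.2.1 for deciding what counts as an AE unchanged.

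The cost is one assay per subject, up to 29 in all, with no new visit or needle stick. Some abnormal results will lead to repeat testing, which under 11.1.1 can itself turn a laboratory finding into a recorded AE.
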